The role of putamen connectivity in emotional health. The putamen's involvement in reward-related behavior and emotions has been well-studied (Lanciego et al., 2012). The basis of hedonic feelings has been studied through many different paradigms demonstrating association with striatal regions including the putamen (Gorwood, 2008). Increased functionality of the putamen is expected to decrease internalizing emotional problems such as feeling unhappy/worried/fearful and induce well-being and a more positive emotional tone. In alignment with this function of the putamen and its stimulation through meditation, our **preliminary results** in healthy adolescents show a decrease in emotional problems (internalizing subscale of the Strengths and Difficulties Questionnaire, SDQ) during the meditation training compared to the waiting period. We also observed in our **preliminary data** an association between the decrease in emotional problems and the increase of the putamen node strength, which provides support for the proposed model (Fig. 1).

[figure not shown]

Figure 2. From left to right: DTI-based whole-brain tractogram in a healthy adolescent (left image); the corresponding graph depicting the connectome with putamen nodes highlighted in red (middle image); tracks connecting the putamen with cortical regions in an adolescent brain (right image).

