9. STATISTICAL CONSIDERATIONS

9.1 General Design Issues

This is a randomized open-label waiting list controlled study of TARA training in 100 boys and girls aged 14-18 years. They will be individually randomized to 12 weeks of group TARA training sessions (50 to TARA training and 50 to waitlist control). The randomization is open label because there was concern that it was not possible to develop a sham training which would motivate participation and yet have no effects on the desired outcomes.

This study is designed to demonstrate that the TARA training will increase putamen connectivity (primary outcome) and decrease emotional problems on the SDQ questionnaire (secondary outcome).

Primary Hypothesis: Putamen structural node strength (primary outcome) will increase in the training group compared to controls.

Secondary Hypothesis: There will be a significant decrease in emotional problems measured with the Strengths and Difficulties Questionnaire (SDQ) (secondary outcome) in the training group compared to controls.

In our recent published study (Yuan et al., 2019), we demonstrated that diffusion MRI connectome methods can provide reliable and precise network measures, including the node strength, in adolescents.

The SDQ was selected because it is widely used in adolescents to measure internalizing problems and has good psychometric properties (Goodman, 2001).

For more details see section 10.3.3 Metrics.

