9.2. Sample Size and Randomization

The study is powered for medium-large effect size of the meditation training on the putamen node strength. With type I error of 0.05, type II error of 0.2 (power of 80%), two-sided effect size of a Cohen's D of 0.6, the required sample size is N=45 subjects who will be studied before and after the TARA training. Given the length of the study (three months), the required commitment to participation in the training, and based on our experience, we assume an attrition rate of 10%; therefore, the target sample size is 50 subjects per group. Our primary analysis will be a general linear model of putamen node strength at week 12 with terms for baseline node strength, treatment assignment and participant sex. The primary analysis will be intent to treat and will include all randomized participants regardless of treatment receipt or protocol violations.

The only clustering in the trial will be the group delivery of the TARA intervention. We anticipate 4 TARA classes of 10-15 participants. We expect the intraclass correlation to be negligible for the following reasons: a) the TARA instructors are trained in standard procedures, b) we expect formidable individual level variation. We therefore did not include cluster assignment in the sample size calculation. We are going to test this assumption in a sensitivity analysis which extended the primary analysis by inclusion of treatment by TARA class interaction.

To standardize TARA delivery, we have included facilitator training and created a very detailed TARA manual (please see Appendix).

Treatment Assignment Procedures

We will use computer-generated randomization with variable blocks sizes of 4, 6 and 8. Individuals will be randomized with no stratification or restricted except the permuted blocks. We will permute 8 blocks of size 8, 2 blocks of size 6, and 4 blocks of size 4. The treatment assignments will be 1:1 within each block and assignments within a block will be permuted. The only masking will be in the administration of questionnaires and in the interpretation of putamen node strength.

The rationale for the use of randomization is to minimize potential biases.

The study is open label to participants, and thus there is no need for unblinding or unblinding procedures.

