Emotional Problems. Our hypothesis is that training will improve emotional problems as assessed by the SDQ T-score compared with controls. We will use an analysis of covariance (ANCOVA) accounting for sex and fit by maximum likelihood. Stata (College Station, TX) will be used to perform data analyses. We will additionally explore age, pubertal status (as determined by the Tanner stage self-report form (Tanner et al., 1962)), and pre-training associations with the changes through an examination of interaction. Potential pre-/post-training differences in movement during MRI will be accounted for by assessing the number of rejected diffusion directions. Sex as a biological variable: In all analyses described, sex will be included as a factor, we will also test for a randomized arm by sex interaction.

In addition, we will examine relationship between changes in node strength of the putamen and changes in emotion by performing a Spearman rank correlation change in node strength through 12 weeks with change in SDQ through 12 weeks.

Other outcomes.

Adherence. We summarize adherence to training including (i) tabulating the number of participants on the training arm who complete at least 75% of sessions, (ii) calculate the minimum, maximum, median and interquartile range of sessions attended by those randomized to the TARA training arm.

Safety and tolerability of the intervention. Adverse events of grade 2 or higher will be tabulated between the arms and compared by the Fisher exact test. Tolerance scores on the CSRS will be summarized (minimum, maximum, median, interquartile range) at each study visiting on the TARA training arm.

We will tabulate the proportion of participants who are retained through 12 weeks and complete the MRI exam and SDQ questionnaire. These will be compared between the arms by the Fisher exact test.

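### The correlation of node-strength change with SDQ change names no analysis set and ignores arm; if the arms are pooled, the treatment effects alone make it negative

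*Combined protocol and SAP*

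**What the plan says.** Section 9.6, under Secondary Outcome, plans to examine how the two changes relate by "performing a Spearman rank correlation change in node strength through 12 weeks with change in SDQ through 12 weeks". The sentence gives no analysis set, no term for arm and no version within arms. The one adjustment stated for every analysis is sex ("In all analyses described, sex will be included as a factor"), which a plain Spearman coefficient cannot carry. Elsewhere the same section writes out a restriction to one arm: the adherence summary concerns "sessions attended by those randomized to the TARA training arm".

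Section 6.1 schedules the MRI and the SDQ at Visit 1 and Visit 14, and Section 6.2.2 has the SDQ taken in every participant, so both changes exist in both arms. Section 9.1 hypothesizes an arm effect on each. For the mechanism: "Putamen structural node strength (primary outcome) will increase in the training group compared to controls". For symptoms: "There will be a significant decrease in emotional problems measured with the Strengths and Difficulties Questionnaire (SDQ) (secondary outcome) in the training group".

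Section 2.2 shows how such a result may be read. In the preliminary data the team saw "an association between the decrease in emotional problems and the increase of the putamen node strength, which provides support for the proposed model".

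**The concern.** Suppose TARA raises node strength and lowers SDQ, but within each arm the participants whose node strength rises most are no more likely to improve. In the pooled sample, TARA participants still tend to have higher node-strength change and lower SDQ change than controls, so the two changes are negatively correlated. That correlation restates the two treatment effects and says nothing about a link within individuals.

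This is the only planned analysis that directly relates the two changes. The artefact runs in the hypothesized direction and grows with the effect on both outcomes. A trial that succeeds on both could therefore report a mechanism link that comes partly or wholly from pooling.

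**Working it through.** **Inputs from the documents.** Section 9.2 gives the design values: "With type I error of 0.05, type II error of 0.2 (power of 80%), two-sided effect size of a Cohen's D of 0.6", and "the required sample size is N=45 subjects who will be studied before and after the TARA training". It also gives 10% attrition, a target of 50 per group and 1:1 allocation. The go/no-go threshold for node strength is d > 0.20 (Section 1.1).

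**Assumptions.** No SDQ effect size is stated, so a range is used. Both effects are in SD units of the change within arm. Changes are normal and independent within arm. The 5% level is used only to give scale; the plan sets none for this correlation.

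**Step 1: the plan's own figure.** A two-sample t-test at d = 0.6, two-sided 0.05 and 80% power needs 44.6 per group, hence 45; 45 / (1 - 0.10) = 50. The stated 45 reproduces as evaluable participants per group.

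**Step 2: correlation produced by the arm effects alone.** Let d1 be the rise in node-strength change and d2 the fall in SDQ change. Under 1:1 allocation the arm indicator has variance 1/4. The pooled covariance is therefore -d1 × d2 / 4, and the pooled variances are 1 + d1²/4 and 1 + d2²/4:

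r = -(d1 × d2 / 4) / √[(1 + d1²/4)(1 + d2²/4)]

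- d1 = 0.6, d2 = 0.2: -0.03 / √(1.09 × 1.01) = -0.029
- d1 = 0.6, d2 = 0.4: -0.06 / √(1.09 × 1.04) = -0.056
- d1 = 0.6, d2 = 0.6: -0.09 / 1.09 = -0.083
- d1 = d2 = 0.2: -0.01 / 1.01 = -0.010
- d1 = d2 = 0.8: -0.16 / 1.16 = -0.138

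If either effect is zero, r = 0.

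**Step 3: rejection rates.** 40,000 simulated trials per row, 45 per arm, no within-arm association, pooled Spearman test at two-sided 0.05. Simulation error is 0.1 to 0.2 percentage points (for example √(0.12 × 0.88 / 40,000) = 0.0016).

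| Node-strength d | SDQ d (assumed) | r from formula | Mean pooled Spearman | Rejected |
|---|---|---|---|---|
| 0.6 | 0 | 0 | -0.001 | 4.86% |
| 0.6 | 0.2 | -0.029 | -0.028 | 5.78% |
| 0.6 | 0.4 | -0.056 | -0.055 | 8.15% |
| 0.6 | 0.6 | -0.083 | -0.082 | 12.05% |
| 0.2 | 0.2 | -0.010 | -0.010 | 5.02% |
| 0.8 | 0.8 | -0.138 | -0.137 | 25.45% |

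In the 0.6/0.6 row, 11.70 of the 12.05 percentage points are rejections in the negative direction. With 50 per arm that row rises to 12.7%.

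**Step 4: alternatives on the same simulated data.** With ranks centred within arm, the mean correlation is about 0 and rejection stays between 4.9% and 5.2% in every scenario. Spearman in the TARA arm alone gives about 0 and 4.9% to 5.1%.

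**The case against.** - **Pooling is inferred.** The plan nowhere says that the arms are combined. The companion analysis in Section 9.6, a Spearman correlation of node-strength change with session attendance, makes sense only in the TARA arm, yet nothing limits it beyond the reference to TARA adherence. Silence is therefore imperfect evidence. This stands: the gap is an unnamed analysis set. Pooling remains the natural reading, because both changes exist in both arms and other parts of the section do name the TARA arm.
- **The size depends on an unknown SDQ effect.** This stands. At the go/no-go threshold on both outcomes, or with no SDQ effect, there is no material inflation. A reader might picture two separated clouds of points, but at d = 0.6 two unit-variance normal distributions overlap by about 76% (2Φ(-0.3) = 0.764).
- **No test is attached.** Section 9.6 gives this correlation no hypothesis, level or decision rule, and the supportive reading in Section 2.2 concerns preliminary data from a comparison of training with a waiting period. This also stands: the rejection rates show scale and do not describe a planned claim. The induced correlation is there with or without a test.
- **The between-arm component belongs to the model.** If TARA works through the putamen, both outcomes should shift by arm, and centring removes that shift. This is true, but the two ANCOVAs already test those shifts. The correlation adds information only through what happens within arms. An arm-adjusted correlation is still open to confounding and is not a full mediation test.

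**Conclusion.** The point holds as a correction to a supporting analysis. As written, the correlation leaves the analysis set and the handling of arm open, and its natural reading lets the arm effects produce a negative value with no individual-level link. At the design effect on node strength the distortion is modest: a correlation of about -0.06 to -0.08, and rejection of about 8% to 12%, for assumed SDQ effects of 0.4 to 0.6. It is negligible for small effects and large only if both effects are well above 0.6. These figures assume normal changes, no within-arm association and 45 evaluable per arm.

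A reader might infer more: that the plan prescribes a pooled analysis, that a false-positive rate near 25% should be expected, or that the trial's error control is damaged. The documents support none of these. The analysis set is unnamed; the 25% figure needs effects of 0.8 on both outcomes, above the design value for node strength; and the primary test, the sample size and the go/no-go criterion do not use this correlation.

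**What to change.** In Section 9.6, state which participants enter the correlation. If all randomized participants with both changes are meant, report a partial Spearman correlation adjusted for arm (ranks centred within arm), together with the correlation in each arm and 95% CIs, and treat these as the evidence for an individual-level link. A pooled coefficient may be shown beside them if it is described as including the between-arm effects. If the TARA arm alone was meant, saying so removes the artefact.

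The cost is a line or two of SAP text and code, with no new data. The adjustment uses about one degree of freedom, will give a smaller correlation than pooling if both effects are real, and drops the between-arm component. The report should say that the adjusted correlation is not a full mediation test. The change should be made before the database is locked and the statistician is unblinded.

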6.2 Description of Evaluations

6.2.1 Screening Evaluation

These evaluations occur to determine if the candidate is eligible for the study.

Definitions of the column headings in the Schedule of Evaluations (Section 6.1): (1) Assessment refers to the specific assessments as listed in the first column that will be performed at each of the study visits; (2) Visit 1 (Day 0) refers to all of the assessments that will occur at the first study visit; (3) Visits 2 to 13 refer to the assessments that will occur at each of the study visits 2 through 13 which correspond to the TARA study intervention sessions 1 through 12 (i.e., Study Visit 2 is TARA study intervention session 1 since the first TARA study intervention session will take place on Study Visit 2); (4) Final Visit 14 refers to all of the assessments that will occur on the final study visit which will be Visit 14. Please note that in the above Schedule of Evaluations (Section 6.1), the AE and SAE forms only will be completed if an AE and/or SAE are reported by a participant. In addition, if a participant prematurely leaves the study, all of the assessments listed under the final study visit 14 column will be performed.

A phone pre-screening evaluation will occur to determine if the candidate adolescent is eligible for the study prior to the initial visit, and a screening evaluation will occur at Visit 1 (Day 0) to determine if the candidate is eligible to enter the study.

Consenting Procedure

A trained research staff member who will have at least a college degree (i.e., Bachelor's degree or higher) will perform the following informed consent process.

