6.2.4 Followup Visits

The following study visits must be performed on the weeks indicated above in the Schedule of Evaluations (please see Section 6.1) plus/minus 5 (five) *working* days (i.e., Monday through Friday, not including weekends and holidays):

- Visit 1:
 - Informed Consent Form
 - Medical History Form
 - Inclusion/Exclusion criteria form
 - Enrollment/Randomization form
 - MRI Screening Form & urine pregnancy test
 - MRI brain scan
 - Demographics assessment (electronically in Qualtrics)
 - SDQ assessment (electronically in Qualtrics)
 - Baseline Checklist
- Visit 2 through Visit 13:
 - Child Session Rating Scale (CSRS)
 - Child Outcome Rating Scale (CORS) including the question: "Has there been any significant unfavorable change in your mental or physical health since last class?" (please see Appendix. Not a source document.)
 - Adverse Events (if answered Yes the question above in CORS)
 - Serious Adverse Events (if answered Yes to the SAE question in the Adverse Event form)
 - On Study Visit Checklist Form (modified to include Treatment Administration information)

6.2.5 Completion/Final Evaluation.

The following assessments will be performed at the participant's final visit (Visit 14):

- SDQ assessment (electronically in Qualtrics)
- MRI Screening Form & urine pregnancy test
- MRI brain scan
- Child Outcome Rating Scale (CORS) including the question: "Has there been any significant unfavorable change in your mental or physical health since last class?" (please see Appendix. Not a source document.)
- Adverse Events (if answered Yes the question above in CORS)
- Serious Adverse Events (if answered Yes to the SAE question in the Adverse Event form)
- Study Completion form.

For study participants who discontinue the study intervention early, all of the following assessments will be performed:

- SDQ assessment (electronically in Qualtrics)
- MRI Screening Form & urine pregnancy test
- MRI brain scan
- Child Outcome Rating Scale (CORS) including the following question: "Has there been any significant unfavorable change in your mental or physical health since last class?" (please see Appendix. Not a source document.)
- Adverse Events (if answered Yes the questions above in CORS)
- Serious Adverse Events (if answered Yes to the SAE question in the Adverse Event form)
- Study Completion form.

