7.2 Methods and Timing for Assessing, Recording, and Analyzing Safety Parameters

The risk profile of our study intervention (TARA) is very minimal. Our institutional IRB has deemed our TARA study intervention to be very minimal risk. Our published peer-reviewed paper using our TARA study intervention in depressed adolescents also demonstrates the exceptional safety and very minimal risk of our TARA study intervention (Henje [name] et al., 2017). The Methods and Timing for Assessing, Recording, and Analyzing Safety Parameters are as follows: (1) At each of the 12 study TARA intervention visits (i.e., TARA visits 1 through 12 [Study visits 2 to 13] as detailed above in section 6.1: Schedule of Evaluations), any and all adverse events will be collected and recorded using the Adverse Event form. Any Adverse Event(s) will be reviewed by the PIs and a determination of the relationship of the Adverse Event to the TARA study intervention will be made by the medical PI ([name]). Based on the study intervention relationship to the Adverse Event as determined by [name] and the severity of the Adverse Event, [name] and [name] will decide upon the appropriate action to take regarding the study intervention (TARA).

If the Adverse Event is classified as Serious Adverse Events, the Serious Adverse Event form will be filled out.

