7.3 Adverse Events and Serious Adverse Events

In the present study, an adverse event and serious adverse event will be defined as follows:

An adverse event (AE) will be defined as any unfavorable and unintended diagnosis, symptom, sign (including an abnormal laboratory finding), syndrome or disease which either occurs during the study, having been absent at baseline, or if present at baseline, appears to worsen. Adverse events will be recorded regardless of their relationship to the study intervention.

A **serious adverse event (SAE)** will be defined as any untoward medical occurrence that results in death, is life threatening, requires inpatient hospitalization or prolongation of existing hospitalization, results in persistent or significant disability/incapacity, or is a congenital anomaly.

Since we do not anticipate any laboratory value changes due to the TARA study intervention, no laboratory values will be collected as part of the current protocol; thus, no laboratory values will be collected to assess safety.

Solicited adverse events will be captured in the following manner: (1) the Child Outcome Rating Scale (CORS) including the following question: "Has there been any significant unfavorable change in your mental or physical health since last class?" will be administered at every TARA session (please see Appendix. Not a source document.); (2) if the participant answers "no" to this question on the CORS, then no additional information will be requested; (3) if the participant answers "yes" to this question on the CORS and the reported event meets the definition of an adverse event given above, then the research assistant or another study staff member will ask the participant for additional details regarding the participant's answer to the CORS question and this information will be recorded in the Adverse Event form within 24 hours of the TARA study intervention session.

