In order to assure that the reporting and data collection systems avoid double capture of solicited and unsolicited events, we have implemented the following items in our protocol: (1) We will ask all of the participants to report any unsolicited events in the CORS after the question, "Has there been any significant unfavorable change in your mental or physical health since the last class?"; (2) If a participant reports an unsolicited event to any of the study staff, the study staff member will ask the participant to write down this information in the CORS in order to avoid double capture of the event; (3) We also will specifically instruct our research assistants and staff to not duplicate the recording (i.e., double capture) of the same solicited and unsolicited events; (4) At the weekly clinical trial research lab meetings, the PIs (Drs. [name] and [name]) will review with the research staff all of the CORS forms, AE and SAE forms for the prior week in order to ensure that there is no double capture(s) of any solicited and unsolicited event(s).

Time Period and Frequency for Event Assessment and Follow-Up

Unanticipated problems will be recorded in the data collection system throughout the study.

To satisfy the requirement for prompt reporting, unanticipated problems will be reported using the following timeline:

- Unanticipated problems that are serious adverse events will be reported to the IRB, Independent Safety Monitors, and NCCIH within 7 days of the investigator becoming aware of the event.
- Any other unanticipated problem will be reported to the IRB, Independent Safety Monitors, and NCCIH within 15 days of the investigator becoming aware of the problem.

All unanticipated problems will be reported to appropriate institutional officials (as required by an institution's written reporting procedures), the supporting agency head (or designee), and OHRP within one month of the IRB's receipt of the report of the problem from the investigator.

Adverse Event Reporting

SAEs that are unanticipated, serious, and possibly related to the study intervention will be reported to the Independent Safety Monitors, IRB, and NCCIH in accordance with requirements.

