7.4 Reporting Procedures

Please see below, Table A, for details of the reporting procedures and timelines, including the individual responsible for each step (e.g., the PIs, the Independent Monitors, etc.). The medical director, [name] (co-PI), will make the decision regarding determining the relatedness and severity of any and all AEs and SAEs. The appropriate AE and SAE forms will be completed. The completed AE and SAE forms will be sent and distributed to the appropriate individual or group of individuals (i.e.,

UCSF IRB, NCCIH) as stated below in Table A (please see below, Table A). The PIs will record all reportable events with start dates occurring any time after informed consent is obtained until 7 days (for non-serious AEs) or 30 days (for SAEs) after the last day of study participation. A research assistant will perform the duties of the Internal QA reviewer. At each study visit, the investigator will inquire about the occurrence of AE/SAEs since the last visit. Events will be *followed* for outcome information until resolution or stabilization.

Table A

Data type	Frequency of review	Reviewer
Subject accrual (including compliance with protocol	Monthly	PIs, Internal QA Reviewer
enrollment criteria)	Semi-annually	Independent Monitors
Status of all enrolled subjects, as	Monthly	PIs, Internal QA Reviewer
of date of reporting	Semi-annually	Independent Monitors
Data entry quality control checks on 100% of charts	Weekly	QA Reviewer
Adherence data regarding study	Monthly	PIs, Internal QA Reviewer
visits and intervention	Semi-annually	Independent Monitors
AEs and rates (including out-of-	Monthly	PIs, Internal QA Reviewer
range lab values)	Semi-annually	Independent Monitors
	Annually	NCCIH
SAEs (unexpected and related)	Per occurrence	PIs, Independent Monitors NIH/NCCIH
SAEs (expected or unrelated)	Per Occurrence	PIs, Internal QA Reviewer
	Annually	Independent Monitors, NIH/NCCIH
Unanticipated Problems	Monthly	PIs, Internal QA Reviewer
	Per Policy	IRB

Reporting Changes in Study Status

During the funding of this study, any action by an IRB, the Independent Monitors, or one of the study investigators that results in a temporary or permanent suspension of the study will be reported to the NCCIH Program Official within 3 business days of notification.

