9.5.2 Secondary Outcomes

The secondary outcomes include the following:

Emotional Problems. Emotional problems will be assessed by the SDQ questionnaire comparing the value before randomization (Visit 1) to the one 12 weeks

after randomization (Visit 14).

Other outcomes

Adherence. The proportion of volunteer randomized to TARA training who participate in at least 75% of the sessions. We expect that at least 80% of participants on the TARA arm will attain this level of adherence.

Safety and tolerability of the intervention. Adverse events will be collected at each visit and graded, and their attribution to their participation will be assessed. The safety of the TARA intervention will be demonstrated if < 15% of the participants experience a grade 2 (moderate) or grade 3 (severe) adverse event related to the TARA intervention.

To demonstrate the tolerability of the intervention used in this study, we will use the Child Session Rating Scale (CSRS) score. The CSRS is a 4-item self-assessments using a 10-cm visual analog scale (Campbell & Hemsley, 2011), with higher scores indicating better experience. This measure of tolerability will be completed after each session. Participants will rate the session in terms of how much they felt listened to, how important the content and activities were to them, how much they liked the session, and their overall experience. The intervention will be tolerable if the median CSRR is at least 20 in >80% of participants.

Retention. To demonstrate the ability to retain subjects, we will retain at least 80% of randomized participants for primary outcome measurement at the end of the study regardless of adherence to the intervention.

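### The Fisher test in Section 9.6 compares adverse events asked about at up to 13 visits in the TARA arm with events asked about once, at Visit 14, in the waitlist arm

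*Combined protocol and SAP*

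**What the plan says.** Section 9.6 (Safety and tolerability) plans a between-arm test: "Adverse events of grade 2 or higher will be tabulated between the arms and compared by the Fisher exact test". It is not restricted to related events and carries no caveat about how events are found.

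Events are found mainly through one item on the CORS: "Has there been any significant unfavorable change in your mental or physical health since last class". Section 7.3 says this "will be administered at every TARA session", and Section 6.2.5 repeats it at Visit 14. Section 7.2 times the recording of events in the same way: "At each of the 12 study TARA intervention visits". Section 6.2.1 refers to "study visits 2 through 13 which correspond to the TARA study intervention sessions 1 through 12", and the schedule in Section 6.1 has a single set of columns with none for the waitlist arm.

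Sections 6.2.4 and 10.1 make the adverse event form conditional on a yes to the CORS item. Section 7.3 sends spontaneous reports to the same form: "the study staff member will ask the participant to write down this information in the CORS".

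Sections 7.4 and 7.5 add a general rule: "At each study visit, the investigator will inquire about the occurrence of AE/SAEs since the last visit". Section 9.5.2 likewise has events collected at each visit, and Section 3 says waitlist participants are followed in a similar way for about 20 weeks. None of these passages names a waitlist contact between Visits 1 and 14.

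**The concern.** A between-arm comparison of event counts means something only if both arms had a similar chance of having an event recorded. Here the main channel is attached to the intervention sessions, and the spontaneous-report channel uses the same form. A waitlist participant with a moderate event in week 3 is first asked about it at Visit 14, by an item whose look-back is the last class. That participant has had no class.

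If waitlist events are under-recorded as a result, an excess in the TARA arm could not be told apart from the effect of more frequent asking. A true excess on the waitlist could be hidden. Waitlist events may also come to light late or not at all, and no later analysis can recover events that nobody asked about.

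The stakes are limited to the reported between-arm comparison. The criterion in Sections 7.1 and 9.5.2 ("The safety of the TARA intervention will be demonstrated if < 15% of the participants" have a related grade 2 or 3 event) and the review trigger in Section 9.4 count intervention-related events. The go/no-go criteria in Section 1.1 rest on effect size and retention.

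**Working it through.** **1. Scheduled inquiries after baseline** (Sections 6.1, 6.2.1, 6.2.5, 7.3)

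- TARA: 12 sessions + Visit 14 = 13 at most. At 75% attendance, 0.75 × 12 = 9 sessions, and 9 + 1 = 10.
- Waitlist: Visit 14 only = 1.
- Look-back: about one week between sessions for TARA. For the waitlist it is the whole interval from Visit 1 to Visit 14, which is at least 12 weeks and up to 12 + 4 + 4 = 20 weeks (Section 3).

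**2. Inputs for the size of the effect**

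The plan states no event rate, capture rate or significance level for this test, so there is no figure of its own to reproduce. From the documents: 50 participants per arm (Section 9.1). Assumed: the same true grade 2+ rate *p* in both arms, capture *c*T for TARA and *c*W for the waitlist, one count per participant, and two-sided p<0.05.

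**3. Bias in the recorded ratio**

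Recorded rate = *p* × capture, so the recorded TARA:waitlist ratio is *c*T / *c*W at any event rate:

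- 100% vs 75%: 1/0.75 = 1.33
- 90% vs 50%: 0.9/0.5 = 1.8
- 100% vs 50%: 1/0.5 = 2.0

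Expected participants recorded at 100% vs 50%:

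- *p* = 20%: 50 × 0.20 = 10 vs 50 × 0.10 = 5
- *p* = 10%: 5 vs 2.5
- *p* = 5%: 2.5 vs 1.25

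**4. Chance of a significant Fisher result with no true difference**

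For every pair of counts (a, b) from 0 to 50, sum Bin(a; 50, *p c*T) × Bin(b; 50, *p c*W) over the pairs where the two-sided Fisher p is below 0.05.

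| Capture, TARA vs waitlist | *p* = 20% | *p* = 10% | *p* = 5% |
|---|---|---|---|
| 100% vs 100% | 2.8% | 1.8% | 0.7% |
| 100% vs 90% | 3.3% | 1.9% | 0.7% |
| 90% vs 75% | 3.7% | 1.9% | 0.5% |
| 100% vs 75% | 6.0% | 2.6% | 0.8% |
| 90% vs 50% | 12.9% | 4.3% | 0.8% |
| 100% vs 50% | 19.5% | 6.3% | 1.2% |
| 100% vs 25% (extreme) | 50.8% | 15.9% | 2.1% |

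At *p* = 20% and 100% vs 50%, 19.47 of the 19.48 percentage points have TARA higher.

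**The case against.** The strongest reply is that several passages apply to both arms. Sections 7.4 and 7.5 record events from consent until 7 days (30 days for SAEs) after last participation and require inquiry at every study visit. Section 7.3 asks all participants to report spontaneous events. Section 3 describes similar follow-up for the waitlist. The case report forms and the monitoring plan were not available and may provide for waitlist contact. So a single waitlist inquiry is inferred from what the schedule omits.

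That is fair as a statement of what is known, but it does not close the gap. A recording window and a rule tied to visits add no contact when the only visits defined independently of TARA sessions are Visits 1 and 14.

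Four further points stand in part:

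- **Size.** It rests wholly on assumptions. Moderate and severe events are the ones most likely to be remembered, and with small capture gaps (100% vs 90%, 90% vs 75%) the test stays below 5% at all three event rates. The large figures need both frequent events and poor waitlist capture. The ratio is biased by any gap, however small.
- **Wording.** For a TARA participant who attends, the last class and the last visit coincide from Visit 3 onward. The mismatch is confined to the waitlist arm, Visit 2 and missed sessions.
- **Importance.** This is one of the other outcomes, below the secondary, in a preliminary open-label study, and no formal decision depends on it. That limits the consequence but does not make the comparison interpretable.
- **Fallback remedy.** Limiting the test to Visit 14 does not fully equalise recall, because TARA participants will have been prompted up to 12 times by then.

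**Conclusion.** The concern holds. As written, the plan specifies up to 13 adverse event inquiries in one arm and one in the other, then tests the counts as if they had been collected alike. The expected direction is against TARA.

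The inquiry counts come from the documents; the size of the bias does not. Under the assumed capture rates, leaving aside the extreme case and the two mild gaps, the recorded ratio is inflated by 1.33 to 2.0. The chance of a spurious significant result at a 20% true rate then runs from 6.0% to 19.5%, against 2.8% with equal full capture. At a 5% true rate it does not exceed 2.1% even in the extreme case, although the ratio remains biased. The change should be made, but it does not bear on the primary outcome, the <15% criterion, the review trigger or the go/no-go decision.

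**What to change.** **Preferred.** Ask waitlist participants the same adverse event item on the same weekly schedule, through the electronic survey system that already collects the SDQ. Word the item identically in both arms with a class-neutral look-back, such as the time since the participant was last asked. Arrange follow-up of yes answers so that outcome assessors stay blinded. The cost is one weekly electronic item for the waitlist arm, staff time for yes answers, and a reworded item in both arms. This changes study conduct as well as analysis text.

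**Otherwise.** Limit the Fisher test to events elicited at Visit 14 in both arms, using one class-neutral question with a common look-back (for example, since Visit 1). Report session-elicited TARA events descriptively. This needs a new Visit 14 question as well as new text in Section 9.6, and it equalises ascertainment only in part because of the earlier prompting.

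**Minimum, if data collection cannot change.** Drop the test, tabulate events by arm and state the unequal ascertainment beside the table. This costs only text and prevents a misleading p-value, but it recovers no missed events.

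In every case, reconcile the CORS look-back to the last class with the look-back to the last visit in Sections 7.4 and 7.5, show the waitlist arm's contacts in the Section 6.1 schedule, and state in Section 9.6 that the count is of participants, if that is intended.
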